Design and Methods: We will recruit 300 people at higher risk of developing liver cancer because of cirrhosis. Study participants will have an ultrasound scan every 6 months as they would in their standard clinical care and an additional 6 monthly non-contrast MRI scan for 30 months (6 visits). If the ultrasound or non-contrast MRI raises concern for a possible liver cancer, an MRI scan with contrast (with dye injection) will be done for definitive diagnosis. All participants will have an MRI with contrast at the end of 30 months to ensure that no cancers were missed. Participants will be asked to complete questionnaires to measure quality of life, anxiety, and their experience of MRI and ultrasound scans and data will be collected from their medical notes. We will compare the number of liver cancers detected by ultrasound to the number detected by the non-contrast MRI scans.

Follow up data will be collected from NHS England, the NHS Central Register for Scotland and other patient registries for up to 10 years after the last study MRI scan to determine the long-term outcomes of participants.

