6. OBJECTIVES AND OUTCOME MEASURES

		Outcome Measures	Timepoint(s)
Primary Objective To evaluate the diagnostic non-contrast enhanced (no ultrasound scans (USS) as s for the diagnosis of hepato (HCC).	ceMRI) and surveillance tools	True positive tests for HCC per round of surveillance False positive tests for HCC per round of surveillance Positive predictive value for HCC per round of surveillance True negative tests for HCC over the 30 months of surveillance False negative tests for HCC over the 30 months of surveillance Sensitivity and specificity of nceMRI and USS for HCC over 30 months of surveillance	Per round of surveillance analysis will be done for each visit: Baseline, visits 2, 3, 4, 5 and 6 For the 30 months of surveillance, analysis will be done for the entire 30 months of surveillance
Secondary objectives			
To determine the stage an diagnosis and the number lesions detected		Numbers of HCC detected by nceMRI and USS at a very early, early, intermediate or advanced stage as defined by the Barcelona Clinic Liver Cancer staging system.	At each 6 monthly surveillance round (Baseline, visits 2, 3, 4, 5 and 6

To determine the proportion of patients that receive treatment with curative intent	The number and size of HCC tumours per participant with HCC The number of new indeterminate lesions identified at each surveillance round Proportion of participants diagnosed with HCC who go on to receive treatment with curative intent	At any time point an HCC is diagnosed, the analysis will be conducted once all participants complete the			
To evaluate the impact of the modality used for HCC surveillance on quality of life (QoL) and anxiety and depression	Results of the EQ-5D-5L questionnaire and Hospital Anxiety and Depression Scale questionnaire	study. At each 6 monthly surveillance round (Baseline, visits 2, 3, 4, 5 and 6			
To evaluate the participants' attitude, experience, and acceptability of nceMRI and USS for HCC surveillance	Results of participant experience questionnaire	Baseline, visit 5			
To evaluate the feasibility of nceMRI and USS as surveillance tools for HCC	Number of missed appointments (cancelled or missed), number of participants lost to follow-up, Number of participants where HCC surveillance is no longer indicated	At the end of the study			

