11.2. Description of the Statistical Methods

Statistical analysis for Primary outcome measure

Measures of diagnostic performance will be determined per round of surveillance and over the 30 months of study participation.

Diagnostic performance per round of surveillance

At each round of surveillance, the following data will be calculated and compared between USS and nceMRI.

- 1. Number and proportions of positive surveillance USS and nceMRI see section 9 for definitions of positive tests
- Number and proportions of true positive (TP) and false positive (FP) USS and nceMRI. As each positive test will be followed by a full contrast enhanced MRI, TP and FP tests per round of surveillance will be calculated
- 3. Positive predictive value (PPV) of USS and nceMRI

Diagnostic performance for the overall study period of 30 months

For the purpose of this analysis, each USS and nceMRI scan for each participant completing the study will be assigned only one of the 4 possible diagnostic categories of: true positive (TP) or false positive (FP), true negative (TN) and false negative (FN). The sum of TP, FP, TN and FN in this analysis will therefore be equal to the total number of participants completing the study. TP and FP will be determined at each visit as described above. TN and FN will be determined at the end of the study when participants undergo the reference standard ceMRI as part of the study protocol. FN results will also include those cases that present with HCC during the study without a prior positive test (interval cancers) or cases where both USS and nceMRI are negative tests but a ceMRI scan is triggered by an AFP>20. Cases that are initially FP may subsequently change diagnostic category. For this analysis, the diagnostic category which is applicable at the end of the study will be used. For example, if a finding initially classed as an FP develops into an HCC that was correctly identified by the surveillance tests, then the diagnostic test will be counted as a TP for this analysis.

Sensitivity and specificity estimates will be calculated separately for nceMRI and USS and compared. Statistical significance of the observed differences in sensitivity/specificity will be evaluated using the McNemar's test of paired proportions, with a two-tailed P-value <0.05 used as the significance criteria.

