11.3. Sample Size Determination

Sample size calculations were performed to estimate a) the minimum number of HCCs and b) patients with cirrhosis and number of HCC needed to detect a difference in sensitivity and specificity between nceMRI and USS. Calculations used McNemar's test for paired proportions (power 90%, type 1 error at 5%). Based on literature, we assumed nceMRI and USS sensitivity of 70-90%⁴³ and 30-50%¹⁸ respectively, and nceMRI and USS specificity of 80%⁴³ and 90%¹⁸ respectively. The calculations suggest that in most scenarios, 50 HCCs and 200 controls would be sufficient to identify a difference in sensitivity/specificity.

Sensitivity		Ultrasound		
		se=30%	se=40%	se=50%
	se=70%	31	54	116
nceMRI	se=80%	21	30	50
	se=90%	14	19	27
Specificity		sp=90%	sp=95%	sp=98%
	sp=80%	244	96	61
nceMRI	sp=90%	NA	530	173
	sp=98%	173	2	NA

Table 2. Minimum number of participants required to demonstrate a statistically significant difference

 in sensitivity/specificity

To observe at least 50 HCCs, the cohort will be enriched with people with a risk of HCC of at least 3% per year (see section 9.4 also). This 3% per year threshold is derived from risk distribution observed among the first 1500 patients recruited to the Pearl cohort. Assuming there will be 2150 participants in Pearl at the time of AMULET inception, and assuming we will continue to see the same risk distribution in the
latter recruited patients as for the first 1500 patients, we determined that selecting patients with a 3year risk of >9% would give rise to 50 HCCs plus ~250-300 controls with liver cirrhosis and no HCC.

Figure 4. HCC risk distribution in Pearl – expected number of HCCs and non HCCs at a >3% annual HCC risk threshold

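### PPV, a primary outcome, is compared only visit by visit; no all-rounds PPV or per-scan false-positive fraction is named, although the same scans would give intervals about 2.4 times narrower

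*Protocol*

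**What the plan says.** The primary objective (Protocol section 6, repeated in the synopsis) has two groups of outcomes. TP, FP and PPV are defined per surveillance round, with this timepoint: "Per round of surveillance analysis will be done for each visit: Baseline, visits 2, 3, 4, 5 and 6". TN, FN, sensitivity and specificity are defined over 30 months.

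Section 11.2 follows the same split. For the per-round block: "At each round of surveillance, the following data will be calculated and compared between USS and nceMRI". The list that follows covers positive tests, TP and FP, and PPV. The 30-month block gives each participant one of TP, FP, TN or FN for each test, so the four counts add up to the number of completers. It compares sensitivity and specificity by McNemar's test, "with a two-tailed P-value <0.05 used as the significance criteria". An early FP that later becomes a correctly identified HCC is recounted as TP. PPV does not appear in this block, nor does any rate per scan.

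Section 11.3 sizes only sensitivity and specificity: "we assumed nceMRI and USS sensitivity of 70-90%⁴³ and 30-50%¹⁸ respectively", and "nceMRI and USS specificity of 80%⁴³ and 90%¹⁸ respectively". It concludes that in most scenarios "50 HCCs and 200 controls would be sufficient to identify a difference in sensitivity/specificity".

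**The concern.** PPV and false alarms per scan determine how many contrast MRIs a surveillance programme generates for each cancer found. Section 5.5 names the consequences of false positives as the main risk to participants.

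Followed as written, the plan gives six separate PPV comparisons, each resting on a handful of cancers, and no overall one. The 30-month block does not fill the gap. A participant with three false alarms counts the same as one with a single false alarm, and some false alarms are reclassified as true positives. A participant-level TP/(TP+FP) could be worked out from those counts, but it is not a listed outcome and does not measure the yield per positive scan. The concern is precision at the level the protocol has chosen, not multiplicity.

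**Working it through.** **1. The plan's own figures.** n = [1.96√ψ + 1.2816√(ψ − d²)]² / d², with ψ = p₁q₁ + p₂q₂ − 2φ√(p₁q₁p₂q₂) + d². Power is 90%, two-sided 5%. The correlation φ is not stated; φ = 0.1 is inferred because it reproduces Table 2.
- Sensitivity 80% vs 50%: ψ = 0.16 + 0.25 − 0.04 + 0.09 = 0.46, n = 49.4, so 50 (printed 50).
- Specificity 80% vs 90%: ψ = 0.16 + 0.09 − 0.024 + 0.01 = 0.236, n = 243.8, so 244 (printed 244).

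Fifteen of the 16 numeric cells reproduce. The exception, 98% vs 95% specificity (printed 2, computed 719), has no bearing here.

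**2. Inputs for one round.**
- HCCs: 50/6 = 8.33 per visit. The even spread is my assumption; the protocol gives no per-visit count.
- HCC-free participants: of 300 recruited, 8.33 leave per round, because section 9.8.1 ends participation at HCC diagnosis. The count falls from 291.7 to 250, with a mean of 271 and a total of 1,625 participant-rounds. Attrition and suspension for LI-RADS 3/4 lesions would lower this further.
- Sensitivity: 80% (nceMRI) and 50% (USS), within the ranges in section 11.3.
- Specificity: section 11.3 does not say whether 80%/90% are per scan or over 30 months, so both readings are shown.

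**3. Reading A: 80%/90% over 30 months, rounds independent.** Per-scan FP is 1 − 0.8^(1/6) = 3.65% and 1 − 0.9^(1/6) = 1.74%.
- TP per visit: 0.8 × 8.33 = 6.67 and 0.5 × 8.33 = 4.17.
- FP per visit: 0.0365 × 271 = 9.89 and 0.0174 × 271 = 4.72.
- PPV: 6.67/16.56 = 40.3% and 4.17/8.88 = 46.9%, a difference of 6.6 points.
- Wald half-widths at one visit: 1.96√(0.403 × 0.597/16.56) = 23.6 points and 1.96√(0.469 × 0.531/8.88) = 32.8 points. For the difference (unpaired approximation): √(23.6² + 32.8²) = 40.4.
- Pooled over six rounds, divide by √6 = 2.45.

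**4. Reading B: 80%/90% per scan.** FP per visit is 54.2 and 27.1. PPV is 6.67/60.87 = 11.0% and 4.17/31.27 = 13.3%.

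**5. Power for the FP difference.** Power = Φ{(d√n − 1.96√ψ)/√(ψ − d²)}, for φ from 0 to 0.3. Reading A: d = 0.0191, ψ = 0.0526 to 0.0379. Reading B: d = 0.10, ψ = 0.26 to 0.188.

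| | One visit (n = 271) | Six rounds pooled (n = 1,625) |
|---|---|---|
| A: PPV half-widths, nceMRI / USS | 23.6 / 32.8 | 9.6 / 13.4 |
| A: PPV difference | ±40.4 | ±16.5 |
| A: FP power | 28–36% | 92–98% |
| B: PPV half-widths, nceMRI / USS | 7.8 / 11.9 | 3.2 / 4.9 |
| B: PPV difference | ±14.3 | ±5.8 |
| B: FP power | 90–97% | about 100% |

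**6. Sensitivity of the result.** The pooled column ignores repeat false alarms in the same person. With an assumed design effect of 1.5 (1,625/1.5 = 1,083), pooled FP power under A is 78–90%. If every participant sat at the 3% entry threshold, 300 × 0.03 × 2.5 = 22.5 HCCs would occur (3.75 per visit). Under A, with about 287 HCC-free participants per round, the PPV difference is then still about ±40 points at one visit and ±16 pooled.

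**The case against.** - **TP and FP are already combined over the six rounds.** A reader might infer from the per-round list that they never are. That is wrong: the 30-month block combines them per participant and tests sensitivity and specificity. By the same formula with φ = 0.1, the 80% vs 90% specificity comparison has 83% power with 200 controls and 91% with 250. This stands, and confines the gap to PPV and the per-scan false-positive fraction.
- **Pooling does not settle PPV.** A reader might infer that a pooled analysis would show which test has the better PPV. It would not: 6.6 points ±16.5 leaves them unseparated. This stands; the gain is a usable interval.
- **A single visit may suffice for false positives.** On reading B it does. Section 11.3 counts participants for a McNemar test, and section 11.2 applies that test to the one-category-per-participant analysis, which favours reading A. Read per scan with independent rounds, 30-month specificity would be 0.8⁶ = 26% and 0.9⁶ = 53%. The protocol does not settle it, so weak single-visit power for false positives cannot be asserted outright.
- **Per-round results may be meant as description, and details belong to the SAP.** Section 11.2 names no test for the per-round block, and section 11.1 defers detail to an SAP that is not shown and might add a pooled PPV. The model specification is SAP material. The level of a primary outcome is not: sections 6 and 11.2 fix PPV at each visit, so an all-rounds PPV would go beyond the outcome as defined.

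**Conclusion.** The point holds in a limited form. PPV is a primary outcome fixed at a level where it can hardly be estimated: about ±40 points on the difference at one visit under reading A and ±14 under reading B, against about ±16.5 and ±6 from the same scans taken together. The per-scan false-positive comparison gains decisively from pooling only if 80%/90% are 30-month specificities (28–36% to 92–98%); otherwise one visit is already adequate.

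These sizes rest on 50 evenly spread HCCs, 80%/50% sensitivity, about 271 HCC-free participants per round and independent rounds; the last makes the pooled figures optimistic. The planned sensitivity and specificity comparison is unaffected. The documents do not support the stronger claim that the primary objective as a whole cannot be answered.

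**What to change.** In section 11.2 and the outcome tables (section 6 and synopsis), add PPV and the per-scan false-positive fraction over all six rounds as the main per-scan comparison. Analyse them paired by test, with participant-clustered standard errors (GEE or a cluster bootstrap) and 95% confidence intervals for the nceMRI–USS contrast. Show baseline separately from visits 2–6, and keep visit-specific figures as description. State in section 11.3 whether 80%/90% are per-scan or 30-month specificities.

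The cost is a wording change and modest analysis work; no further scans or participants are needed. The downside is that the pooled figure averages the prevalent baseline round with the incident rounds, so the baseline split must stand beside it.

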5.5. Potential risks and benefits

If MRI is superior to USS for HCC surveillance participants may benefit from diagnosis of HCC at an earlier stage, which in turn can lead to more effective treatment and better survival.

The main risk to participants will be risks related to false positive results that may lead to unnecessary anxiety, added investigations and possible invasive procedures. The risk of suffering harm during the MRI examination is minimised through safety screening which will be repeated before each scanning session.

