^A contrast enhanced MRI scan may be needed depending on AFP levels (see section 11.2) *Indeterminate lesions will be those that are not definitely HCC and not definitely benign (LI-RADS 3 or LI-RADS 4). The local HCC multidisciplinary team will determine how these are followed up (assessment with alternative imaging modality, interval contrast enhanced scan, biopsy or another follow-up strategy). For the analysis of sensitivity and specificity that will be conducted over the 30 months of follow-up, cases where surveillance tests identified indeterminate lesions, will be counted as true

positives if the lesion progresses to HCC by the end of follow-up and as false positive if they remain indeterminate or are subsequently classed as definitely benign. For the analysis that will be conducted for each surveillance round, the number of indeterminate lesions identified by nceMRI and / or USS will be recorded.

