9.8.1. Description of comparator(s)

The comparator will be the diagnosis of hepatocellular carcinoma based on the typical features on contrast enhanced MRI or CT or histological diagnosis (biopsy or resection) or a consensus diagnosis of HCC as determined by the local MDT will be accepted as a diagnosis of HCC.

On study contrast enhanced MRI scans

For cases where a contrast enhanced MR is done following a positive surveillance test (on study ceMRI), lesions classified as LI-RADS 1 or 2 will be regarded as negative for HCC and lesions classified as LI-RADS 5 will be regarded as positive for HCC. Lesions classified as LI-RADS 3 or 4 will be regarded as indeterminate and will be followed up according to the local clinical routine. If LI-RADS 3 or 4 are designated as HCC by the local MDT, or they are proven to be HCC on biopsy, or they progress to LI-RADS 5 within the 30 months of follow-up then they will be defined as HCC for the analysis relating to the whole 30 month period of surveillance. In cases where LI-RADS 3 or 4 lesions remain under follow-up at the end of the 30 months follow-up without a clear classification as HCC or benign, or where they have been histologically proven to be benign, then they will be classified as negative for HCC for the purposes of the analysis. The classification of lesions at on-study ceMRI scans is shown below in Figure 2. The follow-up of LI-RADS 3 and 4 lesions in this situation will finish at the timepoint that visit 6 was due or at an earlier time point if a definitive classification is reached before then.

Figure 2: Flowchart for the classification of lesions detected on contrast enhanced MRI performed during the study following a positive surveillance test. In cases where lesions are determined as negative within the 30-month surveillance period, participants will re-enter the AMULET surveillance schedule until they complete the study. Where a positive for HCC diagnosis is made, participants will end their participation, will undergo no further surveillance and will be managed according to the recommendations of the local MDT. Participants with LI-RADS 3 or 4 lesions who are undergoing interval contrast enhanced imaging as recommended by the local MDT will be suspended from participation in AMULET.

End of Study contrast enhanced MRI scan

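### The end-of-study category rule in section 11.2 permits a cleared false positive to be scored as a true negative, so 30-month specificity has no single definition

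*Protocol*

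**What the plan says.** In section 11.2, each participant who completes the study gets one category per test for the 30-month analysis. An initial FP may change category, and "For this analysis, the diagnostic category which is applicable at the end of the study will be used". The one worked example is a finding first called FP that develops into an HCC and is then counted as a true positive. The same paragraph settles true and false positives visit by visit. It settles true and false negatives at the end, on the reference contrast MRI. Sensitivity and specificity are then compared by McNemar's test, "with a two-tailed P-value <0.05 used as the significance criteria".

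Four other places bear on the rule:

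- **Section 9.8.1, Figure 2 legend.** When a lesion is judged negative during follow-up, "participants will re-enter the AMULET surveillance schedule until they complete the study".
- **Section 7, Figure 1 footnote.** For the 30-month sensitivity and specificity analysis, indeterminate lesions count "as false positive if they remain indeterminate or are subsequently classed as definitely benign".
- **Section 9.8.1, end-of-study scan.** The final contrast MRI is described for participants who finish all six rounds with no positive surveillance test and no HCC.
- **Section 9.10 and Appendix A.** The visit 6 contrast MRI is for all participants.

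Section 11.3 plans on "nceMRI and USS specificity of 80%⁴³ and 90%¹⁸ respectively". It does not say whether these are per-scan values or per-participant values over 30 months.

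**The concern.** Take a participant without HCC whose nceMRI is positive at round 2, whose contrast MRI shows LI-RADS 1 or 2, and who returns to surveillance. Every later test is negative, and so is the visit 6 contrast MRI. Section 11.2 supports two answers:

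- **FP**, because false positives are settled at each visit.
- **TN**, because TN is settled at the end and the end-of-study category prevails.

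On the second answer, a lesion cleared at once is forgiven. An indeterminate lesion later shown to be benign stays FP under the Figure 1 footnote.

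Specificity over 30 months is part of the primary objective, and section 11.2 also models it by regression in participants without HCC. Section 5.5 says "The main risk to participants will be risks related to false positive results". Under one reading, specificity is the chance of passing six rounds without a false alarm. Under the other it is close to a last-round figure. Two analysts could follow the protocol faithfully and report very different results.

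**Working it through.** **Inputs from the protocol.** Specificity 80% (nceMRI) and 90% (USS), McNemar's test, two-sided 5%, 90% power (section 11.3; 11.2 for sidedness). Six rounds (section 7). 200 controls, with about 250–300 expected (section 11.3).

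**Assumptions not in the protocol.** Between-test correlation 0.1, inferred from Table 2. The same FP risk at each round. Independent rounds, relaxed in step 4.

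**Step 1: reproduce Table 2.** With marginals p1 and p2 and correlation r:

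- covariance = r√[p1(1−p1)p2(1−p2)] = 0.1 × √(0.8×0.2×0.9×0.1) = 0.012
- discordance pd = p1(1−p2) + p2(1−p1) − 2×covariance = 0.08 + 0.18 − 0.024 = 0.236
- difference d = 0.10
- n = [1.960√pd + 1.282√(pd−d²)]² / d² = [1.960√0.236 + 1.282√0.226]² / 0.01 = 243.8, so 244

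Table 2 gives 244. The same formula with r = 0.1 matches 15 of its 16 numeric cells. The other cell (98% against 95%) reads 2 and computes to 719; that may be a text-extraction fault and is not used here. With r = 0 the 80%/90% cell would be 270.

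Power = Φ{[d√n − 1.960√pd] / √(pd−d²)}. For 80% against 90% this is 91% at 250 controls and 83% at 200.

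**Step 2: suppose 80%/90% are 30-month any-FP values.** The per-round specificities are 0.80^(1/6) = 0.9635 and 0.90^(1/6) = 0.9826. Among 250 participants without HCC:

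- any-FP scoring: 250×0.20 = 50 (nceMRI) against 250×0.10 = 25 (USS) FP participants
- last-round scoring: 250×0.0365 = 9.1 against 250×0.0174 = 4.4

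The 10-point difference becomes 1.9 points, with pd = 0.0477. Power is 28% at 250 controls and 23% at 200, and 1371 controls would be needed for 90%.

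**Step 3: suppose 80%/90% are per-round values.** Last-round scoring gives 80% and 90%. Any-FP scoring gives 0.80⁶ = 26.2% and 0.90⁶ = 53.1%. Planned power is not lost here: last-round scoring keeps the planned 10-point difference, and any-FP scoring widens it to 26.9 points. What changes is the specificity reported.

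**Step 4: allow correlation between rounds.** With per-round FP risk m of 20% or 10% and a beta-binomial model, P(no FP in six rounds) = B(a, b+6)/B(a, b), where a = m(1−ICC)/ICC and b = (1−m)(1−ICC)/ICC. The last column is the share of participants with any false alarm whom last-round scoring would count as TN.

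| ICC | Ever FP, nceMRI / USS | FP at last round | Share lost, nceMRI / USS |
|---|---|---|---|
| 0 | 73.8% / 46.9% | 20% / 10% | 73% / 79% |
| 0.3 | 51.4% / 29.4% | 20% / 10% | 61% / 66% |
| 0.5 | 40.8% / 22.3% | 20% / 10% | 51% / 55% |
| 0.7 | 31.7% / 16.8% | 20% / 10% | 37% / 40% |

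Last-round scoring is an outer limit, because false positives covered by the Figure 1 footnote stay FP on either reading. The protocol gives no LI-RADS split from which to size that share.

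**The case against.** The strongest reply is that a change from FP to TN is written nowhere. The only illustrated change is to true positive, and FP status is settled at each visit. Section 9.8.1 describes the final contrast MRI for participants never positive, so TN could be meant for them alone. Section 11.8 likewise speaks of a contrast MRI either after a positive test or at the end. On that reading, sections 7 and 11.2 agree. This stands to the extent that the protocol permits FP to TN and does not prescribe it. It does not settle the matter. The rule is worded generally, its example is offered only as an example, and section 9.10 and Appendix A give everyone the final scan on which TN is decided.

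A second reply is that false alarms stay visible, because FP counts and positive predictive value are reported for every round. That is correct, so a reader who infers that the plan conceals them goes too far. But per-round counts do not give the cumulative per-participant specificity, and they are not what the 30-month McNemar test compares.

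A third reply is that false positives may recur in the same people, which narrows the gap; step 4 shows this. Against strong recurrence, section 9.8.2 does not treat lesions already diagnosed as benign as suspicious on nceMRI, and definitely benign findings on USS are negative.

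A fourth reply is that the SAP may settle the point. It may, but the protocol already fixes a rule that its own text contradicts, and the SAP would inherit the conflict.

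**Conclusion.** The concern holds as an unresolved conflict in how a primary outcome is defined. For a participant without HCC whose false positive is cleared and who finishes negative, the protocol supports both FP and TN, and the choice largely determines 30-month specificity. Under the stated assumptions, nceMRI and USS specificity are 80%/90% or 96.3%/98.3% on the 30-month interpretation, and about 26%/53% or 80%/90% on the per-round interpretation. The power loss, from about 91% to 28% at 250 controls, belongs to the 30-month interpretation only. These figures also rest on equal, independent risk per round and the inferred correlation of 0.1.

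A reader might infer two stronger claims that the documents do not support:

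- **That the rule hides most false alarms.** This needs the FP-to-TN reading and, in the per-round scenario, an intraclass correlation no higher than about 0.5.
- **That it favours nceMRI disproportionately.** More nceMRI participants would be reclassified in absolute number. But the share reclassified is slightly larger for USS in every scenario: 82% against 83% in step 2, and as tabulated in step 4.

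**What to change.** In section 11.2, and in the SAP, state that:

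1. In participants without HCC at the end of the study, a test is FP if it was positive at any round and TN only if it was negative at every round.
2. Participants with HCC by the end of the study are classed, for each test, as true positive or false negative according to whether that test detected the HCC, whatever earlier false positives they had. This keeps a participant with an early benign false alarm and a later, separate HCC in the sensitivity analysis.
3. Last-round status, if wanted, is reported separately and labelled as such.

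If the investigators do intend FP to become TN, the protocol should say so explicitly and name the result a last-round measure.

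Then reconcile section 11.2 with the Figure 1 footnote, and section 9.8.1 with section 9.10 and Appendix A on who has the end-of-study contrast MRI. In section 11.3, say whether 80% and 90% are per-scan or 30-month per-participant values.

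The cost is a few sentences, settled before any analysis. The reported 30-month specificity will look less favourable for both tests than under last-round scoring.
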